5.1 Description

The study drug, IVIG-eye drops, will be compounded in the UIC Eye and Ear Infirmary (EEI) Pharmacy and supplied as a 4 mg/ml (0.4%) preservative free solution in single use vials for administration as topical eye drops. The control group will receive Normal saline eye drops as placebo.

Each subject will receive either IVIG-eye drops (study drug) or Normal saline (placebo) solution, as a single eye drop in each eye two times a day (BID) for eight weeks. Except for the first dose on Day1, subjects will self-administer the test medication eye drops at home.

Subjects will not be charged for the test medication in any way (neither the cost of the medication nor its dispensing cost).

5.2 Treatment Regimen

Study drug group- IVIG-eye drops, 4mg/ml eye drops will be applied to both eyes b.i.d for 8 weeks. Control group – Normal saline eye drops will be applied to both eyes b.i.d for 8 weeks. For either group, the subject will be instructed to instill the first dose of the study medication in the morning at approximately 8 a.m., and then the other dose at approximately 12 hour interval. Therefore, doses will be scheduled at approximately 8 a.m. and 8 p.m.

5.3 Method for Assigning Subjects to Treatment Groups

This Randomized placebo-controlled trial will have two study groups. Subjects will be randomly assigned to one of two groups (#1, #2). One group will receive the study drug (IVIg 4mg/ml; test group), and the other group will receive placebo (Normal saline; control group). We will use a computer-based random code generator (Research Randomizer; <http://randomizer.org/>) to generate 1 set of 24 non-unique, unsorted numbers with a range from 1 to 2 representing the group number (#1/ #2). Each subject will be assigned a study identification (ID) number at screening, e.g. Subject #1, subject #2, and subject #3 and so on. Based on the randomizer generated table, subject #1 will receive either placebo or study drug. This will be repeated for each subject. For reproducibility purpose, we will document the final randomization schedule and the random SEED number used to generate the schedule. Randomization will be performed by the Illinois Eye and Ear Infirmary's pharmacy, and neither participants nor research staff will be aware of the assigned treatments. The person conducting the randomization will remain masked as well.

The study identification (ID) number will be used on all study-related documents. The drug vial number will be linked to the subject identification number.

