Objectives	To evaluate the safety and preliminary efficacy of IVIG-eye drops in patients with Dry Eye Disease.
Number of Subjects	24 (study drug- 12, placebo- 12)
Diagnosis and Main Inclusion Criteria	Men and women ≥ 18 years of age with a diagnosis of Dry Eye Disease, with Schirmer's test ≥ 0 to ≤ 9 mm/5min, Ocular surface staining ≥ 1 and OSDI mild (≥ 13), with high ACPA (> 4.4 units) in ocular surface wash
Study Product, Dose, Route, Regimen	Study drug : Intravenous Immunoglobulin (IVIG), 4 mg/ml (0.4%) eye drops two times a day for eight weeks. Control : Normal Saline Eye Drops (0.9% NaCl)
Duration of administration	8 weeks
Reference therapy	Normal Saline eye drops two times a day for eight weeks.

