3.1 General Design

This will be a Randomized controlled trial, in which a total of 28 subjects will be enrolled at 1 clinical site. Subjects will be randomly assigned to one of two groups (#1, #2), with 14 subjects per group. One group will be given placebo (Normal saline eye drops) and the other group will be given eye drops containing the study drug (IVIG).

Patients with established Dry Eye Disease will be approached by a member of the research staff to determine if he/ she might be interested in participating in a research study. If the subject is interested, the research staff member will describe the study. If the subject is willing to enter the study, the study will be discussed and the subject will be asked to sign the informed consent form. Consent will be obtained prior to screening to determine eligibility. Screening procedures include documentation of Dry Eye Disease. Eligible subjects will be enrolled in the study.

All enrolled subjects will receive their first dose of test medication (placebo/ study drug) on study Day 1 in the doctor's office, and after completion of the study assessments, will have the topical eye drops dispensed for self-administration. See Section 5.4 *Preparation and Administration of Study Drug* for details.

Subjects will be provided with diaries to record the time of each dose and will also be asked to record any adverse symptoms. In addition, they will be asked to make a note of any missed doses together with the reason for the omission. Subjects will return at 4 weeks for further study assessments,

thereafter at 8 weeks (the last day of treatment), and again at 10 weeks after two weeks of no treatment with study drug for the final study assessments.

There is no primary efficacy endpoint in this study. Instead several exploratory efficacy endpoints will be assessed.

The primary tolerability endpoint is the change in the test substance tolerance between Day 1 (post-dose) and 8 weeks (56 days).

[figure not shown]

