6.3 Screen Failure

A record of screen failures and the reasons for non-eligibility to the study will be maintained.

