7.1 Sample Size Determination

As this is a feasibility trial intended to guide the planning of larger future investigations, there are no formal sample size calculations.⁶⁵ The aim of the study is to recruit a sufficient number of patients to evaluate the acceptability and safety of the intervention and the study design. An outcome of this study will be to estimate parameters such as the SD for a sample size calculation of a subsequent full-scale trial. A sample of 24 patients (12 in each arm) is considered adequate for obtaining reliable sample size estimates.^{66, 67} To allow for a conservative attrition rate of 10%, we aim to recruit 28 patients into the trial.

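### The randomisation list has 24 unrestricted entries read by screening number, so it cannot allocate 28 subjects as 14 and 14

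*Combined protocol and SAP*

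**What the plan says.** Section 5.3 builds the allocation table with a web-based generator as "1 set of 24 non-unique, unsorted numbers with a range from 1 to 2 representing the group number". It states no block size, no restriction and no required number of ones and twos.

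The same section fixes how the table is used: "Each subject will be assigned a study identification (ID) number at screening", numbered in sequence from 1, and then "Based on the randomizer generated table, subject #1 will receive either placebo or study drug", and so on for each subject. Section 6.2 repeats that the number is given at screening. Section 6.5.2 places randomisation later, at Visit 2.

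The planned size differs between sections:

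- Study Summary: 24 subjects, 12 per arm.
- Section 3.1: a trial "in which a total of 28 subjects will be enrolled at 1 clinical site", and "Subjects will be randomly assigned to one of two groups (#1, #2), with 14 subjects per group".
- Section 7.1: 24 (12 per arm) is judged adequate; to allow for 10% attrition, "we aim to recruit 28 patients into the trial".

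Screen failures are expected. Section 6.3 states: "A record of screen failures and the reasons for non-eligibility to the study will be maintained". Section 3.5 makes the proportion of screened subjects who are recruited an endpoint. Section 8.1 allows subjects who withdraw because of an adverse event to be replaced.

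**The concern.** One rule has three faults.

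1. **Length.** The list has 24 entries for 28 subjects and none for replacements.
2. **Balance.** Repeated draws of 1 or 2 with no constraint amount to coin-toss randomisation. Nothing in the rule produces 12:12 or 14:14.
3. **Indexing.** The entry is tied to a number issued before eligibility is known. A subject who fails screening takes an entry out of use, so the list runs out sooner.

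Section 7.1 rests its size on 12 per arm, and Section 7.2 reports rates with 95% confidence intervals by treatment group. Arm size is therefore the basis of the planned precision, and the procedure does not control it. Staff who follow the text also reach a subject with no allocation and must extend the list during the trial, by a method the protocol does not describe. Section 5.3 promises one documented schedule and seed.

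**Working it through.** **Reproducing the target of 28.** Inputs from Section 7.1: 12 per arm, 10% attrition. 12 / (1 − 0.10) = 13.3, rounded up to 14 per arm, so 28 in total. The plan's figure reproduces; 28 is not in error.

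**Length.** 28 subjects (Sections 3.1 and 7.1) − 24 entries (Section 5.3) = 4 subjects without an allocation, with no screen failures and no replacements. No section extends the list or adds a second one.

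**Balance.** Let X be the number allocated to one arm, with independent draws at probability 1/2, so X ~ Binomial(n, 0.5).

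- n = 24: P(exactly 12:12) = C(24,12) / 2^24 = 2,704,156 / 16,777,216 = 16.1%.
- n = 28, list extended the same way: P(exactly 14:14) = C(28,14) / 2^28 = 40,116,600 / 268,435,456 = 14.9%.
- Unequal splits: P(smaller arm ≤ k) = 2·P(X ≤ k).

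| Entries | Split | Probability |
|---|---|---|
| 24 | 10:14 or worse | 54.1% |
| 24 | 9:15 or worse | 30.7% |
| 24 | 8:16 or worse | 15.2% |
| 28 | 12:16 or worse | 57.2% |
| 28 | 11:17 or worse (one arm below 12) | 34.5% |

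**Adding the plan's own attrition.** Assume each subject drops out independently with probability 0.10. From 14 per arm, P(at least 12 remain in one arm) = P(Binomial(14, 0.9) ≥ 12) = 0.842, so for both arms 0.842² = 0.71. Averaging the same calculation over coin-toss splits of 28 gives 0.33.

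**Screen failures.** The documents give no rate, so f is an assumption. Expected randomised subjects from 24 numbers = 24(1 − f). Entries needed to randomise 28 on average = 28 / (1 − f), rounded up.

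| Assumed f | Randomised from 24 numbers | Entries needed for 28 |
|---|---|---|
| 10% | 21.6 | 32 |
| 20% | 19.2 | 35 |
| 30% | 16.8 | 40 |
| 40% | 14.4 | 47 |
| 50% | 12.0 | 56 |

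**Would a list fixed at 12:12 solve it?** Not while it is read by screening number. If k entries are skipped at random, exact balance survives with probability C(12, k/2)² / C(24, k): 144 / 276 = 52% for k = 2, and 4,356 / 10,626 = 41% for k = 4.

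**The case against.** The four missing entries are hard to dispute. The case against the rest runs as follows.

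- **Coin toss is a reading.** A list fixed at 12:12 would also contain repeated, unsorted numbers. This stands as a point about wording: on balance alone, the exact statement is that the rule does not guarantee equal arms. The text states no constraint, however, so independent draws are the natural reading. Simple randomisation is also a valid, unbiased method.
- **Imbalance costs little here.** Relative to 12:12, the standard error of a difference in means is multiplied by √[(1/a + 1/b) / (2/12)]: up 1.4% at 10:14, 3.3% at 9:15 and 6.1% at 8:16. A pooled SD keeps 22 degrees of freedom at any split of 24. With no events in an arm, the exact upper 95% limit, 1 − 0.025^(1/n), moves from 26.5% (n = 12) to 30.8% (n = 10). Section 7.2 plans no efficacy tests. These figures are right and show that imbalance alone would not undermine a feasibility trial. They do not supply the missing allocations.
- **Attrition, not the list, may cause the shortfall.** Even 14:14 keeps 12 in both arms only about 71% of the time. That is so, but the coin-toss rule lowers it to about 33%.
- **Allocation integrity is not much threatened.** The pharmacy randomises and clinic staff are masked (Section 5.3), so further independent draws would reveal nothing to the clinic. This stands: the risk is mild and lies in an undocumented procedure.
- **Screen failures may be few.** Candidates must have diagnosed dry eye and a past positive antibody value (Section 4.3), and some clinic patients skip formal screening (Section 6.5.1). This may shrink the loss but does not remove it. The 50% end of the range is illustrative. Section 8.8 calls the study numbers random, which conflicts with the sequence in Section 5.3 and also needs clearing up.

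**Conclusion.** The concern holds. Followed as written, Section 5.3 leaves at least four of 28 subjects without an allocation. That is a count from the protocol's own figures and rests on no assumption.

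The lack of balance rests on reading the list as independent draws: 16.1% for 12:12 in 24 and, if lengthened to 28 the same way, a 34.5% chance that an arm starts below 12. The loss through screening numbers follows from Sections 5.3 and 6.2; its size depends on a failure rate that the documents do not give.

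This must be corrected before the first subject is randomised. The reason is that the procedure cannot be carried out for the planned sample; the precision lost through unequal arms is modest.

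**What to change.** Rewrite the allocation paragraph in Section 5.3 and regenerate the list:

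- Use a 1:1 permuted-block list with small, varying block sizes that are not disclosed to the clinic.
- Provide at least 28 allocations, 14 per arm, plus spares for the replacements that Section 8.1 allows. The pharmacy generates and holds the list, with schedule and seed documented as already planned.
- Assign the next unused randomisation number at Visit 2, after eligibility is confirmed. Keep it separate from the screening number, so that screen failures use no entries.
- Make the Study Summary and Sections 3.1, 5.3 and 7.1 agree: 28 randomised to obtain 24 evaluable. Bring Sections 6.2 and 8.8 into line on how study numbers are issued.

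The cost is one paragraph, a new list and these edits for consistency. No extra patients or staff are needed. Blocking does not protect against dropout, but under the plan's 10% attrition it raises the chance of keeping 12 in both arms from about 33% to about 71%.

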5.4 Preparation and Administration of Study Drug

The study medications will be stored, packaged and dispensed from the UIC Eye and Ear Infirmary (EEI) Pharmacy. No modifications, except dilution with preservative free normal saline to achieve 4mg/ml concentration, will be made to the study medication constituents. The drug and placebo will be dispensed in sterile eye droppers as single use vials, as explained below:

The study medications will be dispensed in sterile eye droppers of 3.0 ml volume. The commercially available product (Flebogamma or an equivalent IVIG preparation) is a single-use ampule containing 5% (50mg/ml) concentration of IVIG. Flebogamma (5%) will be diluted in normal saline to achieve IVIG-eye drops 0.4% (4mg/ml). 0.5 ml to 1.0 ml of IVIG-eye drop (4mg/ml) will be transferred into one sterile eye droppers of 3.0 ml volume. IVIG-eye drops preparation (by diluting Flebogamma) will be done at Illinois eye and ear infirmary (EEI) pharmacy, under standard aseptic precautions. The eye droppers will be used by subjects as single-dose applications.

One drop of the drug/ placebo solution will be administered to each eye. Therefore, 2 eyedroppers will be required per day. **At each visits, subjects will receive 56 sterile multi-dose eye droppers that will be used as single-dose applications for 28 days.** Prepared eye droppers will be placed in a dark (brown) colored zip-lock packet before being dispensed to the subject. The medication can be stored at room temp, away from direct strong light.

Instructions for Drug Use:

1. Wash your hands thoroughly with soap and water.
2. Check the dropper tip to make sure that it is not chipped or cracked.
3. Avoid touching the dropper tip against your eye or anything else – eye drops and droppers must be kept clean.
4. While tilting your head back, pull down the lower lid of your eye with your index finger to form a pocket.
5. Hold the dropper (tip down) with the other hand, as close to the eye as possible without touching it.
6. While looking up, gently squeeze the dropper so that a single drop falls into the pocket made by the lower eyelid. Remove your index finger from the lower eyelid.
7. Close your eye for 2 to 3 minutes and tip your head down as though looking at the floor. Try not to blink or squeeze your eyelids.
8. Place a finger on the tear duct and apply gentle pressure.
9. If you are to use more than one drop in the same eye, wait at least 5 minutes before instilling the next drop.
10. Do not reuse the dropper after use. Use another dropper for next dose.

The subject should repeat the above procedures for the other eye to demonstrate to the Investigator or designee that they are able to perform the drug administration satisfactorily. Subjects will be instructed to perform these steps on each administration of the study medication. Instructions for use will be included in the zip-lock packet with the study medication and site personnel will ensure that these instructions are given to the subject.

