5.8 Packaging

The study medications will be dispensed in sterile eye droppers of 3 ml volume, which will be used as single-dose applications. One drop of the placebo/ drug solution will be administered to each eye. Therefore 2 eye droppers will be required per day because the placebo/drug is administered two times a day. At each visit, subjects will receive 56 sterile eye droppers that will be used as single-dose applications. The eye droppers will be placed in a dark (brown) colored packet before being dispensed to the subject. A label with abbreviated information will be placed on each eye dropper. The zip-lock packet will include the subject's name, stage of visit, instructions for drug use and storage and the drug expiration date. The label will also include the study name (abbreviated) and a statement that the drug is **investigational** for use only in this research study." The first dose will be administered to the subject by the researcher from one of the eye droppers that will be dispensed to the subject at the first treatment visit (visit 2, day 1). No separate packing will be done for the study medication to be used in the MD's office. The subjects will receive the 4 weeks of remaining doses in a dark packet to take home. 56 sterile eye droppers will be dispensed at each visit.

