5.9 Receiving, Storage, Dispensing and Return

5.9.1 Receipt of Drug Supplies

The UIC Investigational Drug Service (IDS) or EEI Pharmacy will order the study drug. The study drug will be stored in the Taylor Street/ EEI pharmacy and dispensed to subjects as needed.

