5.9.3 Dispensing of Study Drug

At the first treatment visit (day 1), the first study medication dose will be administered to the subject in the clinic and eye droppers sufficient to last for 4 weeks will be given to them to take home. The subjects will be asked to return the used and unused eye droppers at the follow-up visits. We will then retrieve the previously -dispensed eye droppers and a fresh 4 week supply will be dispensed by the pharmacy. This will be done at first treatment visit (day 1) and week 4. No new drug eye droppers will be given on the week 8 visit.

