6.5.3 Visit 3: Week 4 (\pm 4 days)

Treatment Visit (after any dose for that day)

- Review the subject's diary and record changes in concomitant medication, deviations from drug schedule and adverse events.
- Vital Signs: Blood pressure, Pulse, and Temperature taken while subject is in a sitting position.
- Visual Acuity (Snellen's chart) with eye glasses (if applicable)
- OSDI
- Symptom Intensity Assessment, SGA and CGA
- Test Substance Tolerance (VAS)
- Baseline Ophthalmic Examination (slit lamp examination, VBR)
- *Dispensing of study drug/placebo (by Pharmacy to patient)*
- *Returning of unused study drug/ placebo (by patient to pharmacy)*

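### Each kit holds exactly 28 days of single-use droppers, but Week 8 may fall more than 28 days after Week 4, so a fully adherent subject can reach the Week 8 tolerability rating with no drug left

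*Combined protocol and SAP*

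**What the plan says.** Section 5.2 sets the regimen: "4mg/ml eye drops will be applied to both eyes b.i.d for 8 weeks", with doses at about 8 a.m. and 8 p.m. Section 5.4 states two droppers a day and the kit size: "subjects will receive 56 sterile multi-dose eye droppers that will be used as single-dose applications for 28 days". The instructions for use in the same section add: "Do not reuse the dropper after use. Use another dropper for next dose".

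The clinic dose on Day 1 is not extra. Section 5.8 says: "The first dose will be administered to the subject by the researcher from one of the eye droppers" in the subject's own kit. Nor is anything carried over. Section 5.9.3 says: "We will then retrieve the previously -dispensed eye droppers and a fresh 4 week supply will be dispensed by the pharmacy". It names Day 1 and Week 4 as the dispensing visits and adds: "No new drug eye droppers will be given on the week 8 visit".

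Sections 6.5.3 and 6.5.4 give Week 4 and Week 8 a window of ±4 days each. Section 3.1 makes the change in the tolerance VAS from Day 1 post-dose to 8 weeks the primary tolerability endpoint, and Section 3.2 has the VAS completed after the test medication is given.

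**The concern.** The supply is fitted to the nominal calendar, while the visits may move. A subject who takes every dose and attends inside both windows can still arrive at Week 8 with no dropper. That subject cannot give the rating as Section 3.2 describes it and has to recall an older dose. The subjects exposed to this are the most adherent ones, since missed doses leave spares.

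A second effect follows when Week 4 is early. The unused part of kit 1 is handed back and kit 2 ends before Day 56, so the plan itself prevents the full 56 days of twice-daily dosing that Section 3.5 counts as completion. The dropper count would not show this, because a subject who ran out returns no unused droppers and looks like a full user.

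**Working it through.** **Day count.** Week 4 and Week 8 are taken as 28 + d4 and 56 + d8 days after Day 1, with d4 and d8 whole days from −4 to +4, giving 9 × 9 = 81 date pairs. Two doses are taken on Day 1. The documents do not state the anchor of the windows.

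**1. The plan's own figure.** 2 droppers/day × 28 days = 56. This reproduces Section 5.4 exactly, with 0 spare.

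**2. Interval to cover.** Shortest: 52 − 32 = 20 days. Longest: 60 − 24 = 36 days. If Week 8 is counted from the actual Week 4 visit: 28 ± 4 = 24 to 32 days.

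**3. Last dose of kit 2.** If kit 2 starts on the evening of the Week 4 visit, its 56th dose falls on the morning 28 days later. A visit at day +28 has a same-day dose and one at +29 has none. At +36 the last dose is 36 − 28 = 8 days old; with the other anchor the maximum is 32 − 28 = 4 days. If kit 2 starts on the morning of the Week 4 visit, its last dose is the evening of day +27, and a visit at +28 already has none.

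**4. Date pairs affected (kit 2 started in the evening).** Run-out requires d8 > d4: 8+7+6+5+4+3+2+1 = 36 of 81.
- Week 4 early (d4 < 0): 8+7+6+5 = 26. Drug ends before the earlier of Day 56 and the visit.
- Week 4 on time or late: 4+3+2+1 = 10. Kit 2 lasts to Day 56, and what is missing is the same-day dose.

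If kit 2 were opened on the visit morning for all five on-time or late Week 4 dates, the five pairs with d8 = d4 would be added: 36 + 5 = 41.

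**5. Dose shortfall from an early Week 4.** With Week 4 k days early, the most doses possible is 2(28 − k) + 1 + 56, which is 111, 109, 107 or 105 of 112 for k = 1 to 4. In the worst case 56 of the 2 × 32 = 64 doses due from Week 4 to Day 56 can be taken (87.5%). If Week 4 is instead study Day 28, which is 27 days after Day 1, each cap is two lower: 109, 107, 105 and 103, with 111 when on time.

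**6. Kit 1.** With two doses on Day 1, the 56th dropper is used on the evening 27 days after Day 1. An on-time Week 4 morning would need a 57th (2 × 28 + 1). Kit 1 therefore lacks a morning dose on 5 of 9 Week 4 dates, on time or late.

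**7. How often, under assumptions.** Neither visit timing nor adherence is given. Three independent in-window patterns were tried: uniform; normal weights with SD 1.5 days; and 60% on the target day with 5% on each other day. The number of doses taken is binomial with n = 2(28 + d8 − d4) − 1, and a subject has run out at 56 or more. For the earlier-of-Day-56 count, d8 is replaced by min(0, d8). Kit 2 starts in the evening.

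| Adherence | No same-day dose at Week 8 | Run-out before the earlier of Day 56 and the visit |
|---|---|---|
| 100% | 31–44% | 17.5–32% |
| 90% | 9–21% | 3–9% |
| 80% | 0.5–4% | at most 0.4% |

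**The case against.** The strongest reply is that little is lost. After Day 1 all dosing is at home, so every Week 8 rating already recalls an earlier dose. The VAS item asks about comfort on instilling the drop and sets no recall period, and Section 6.5.4 allows for a visit day without a dose. The contrast is hours against days of recall, in someone who has used the drop for weeks. This stands and limits the weight of the point, but it does not reconcile the kit with Section 3.2.

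Treatment is also defined as 56 days, so a visit after Day 56 is off drug by design. That is right for 10 of the 36 pairs; the other 26 end early.

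Section 5.6 speaks of monitoring at 4-week intervals, which suggests booking from the previous visit. The range is then 24 to 32 days: narrower, but still beyond 28.

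Three phrases might seem to supply a remedy. Section 5.9.1 has drug "dispensed to subjects as needed", but Section 5.9.3 names only two dispensing visits. The droppers are called multi-dose, but reuse is forbidden. The allowance for a dose-free visit day permits the visit, not a rating after administration.

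A run-out would not pass unseen either. Diaries hold dose times and reasons for missed doses, and at Weeks 4 and 8 staff "record changes in concomitant medication, deviations from drug schedule and adverse events".

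**Conclusion.** The mismatch is real and follows from the protocol's own numbers: 28 days of supply against an interval of up to 36 days, or 32 under the other anchor. A fully adherent subject seen more than 28 days after Week 4, or at 28 days if kit 2 was opened on the visit morning, rates Week 8 tolerability from a dose 1 to 8 days old at most. The effect is modest. The rating is degraded, not lost; both arms are affected alike; Section 7.2 rules out efficacy tests, and no test or threshold rests on this rating. The point merits a small correction and no more.

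A reader might infer three stronger things that the documents do not support:
- That about 44% of subjects will be affected. The 36 of 81 is a count of date combinations. Every percentage rests on assumed visit patterns, and the percentages fall sharply once doses are missed.
- That the comparison between arms is biased or the endpoint invalid. Supply and windows are the same in both arms, and nothing in the documents sizes the effect of a few days' recall on the VAS.
- That a 28-day booking rule alone removes the problem. It does not when kit 1 is already empty and kit 2 starts on the Week 4 morning.

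**What to change.** Choose one.

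**(A) Supply to the latest in-window visit.** In Sections 5.4, 5.8 and 5.9.3, dispense 66 droppers at Day 1 (2 × 32 + 1 = 65, rounded up to an even number) and 73 at Week 4 (2 × 36 = 72, plus one if that morning's dose is still due). State in Section 5.2 and the synopsis that dosing continues through the morning of the Week 8 visit. The cost is at most 10 + 17 = 27 extra droppers per subject. For a 14-subject IVIG arm that is 378 droppers of 0.5 to 1.0 mL, or 189 to 378 mL at 4 mg/mL: 0.76 to 1.5 g IgG, about 15 to 30 mL of the 50 mg/mL product. The placebo arm needs the same number of saline droppers. The pharmacy must confirm expiry to 36 days, and exposure may extend by up to 4 days.

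**(B) Constrain the booking.** Issue 58 droppers at Week 4 (57 cover a morning start through the morning of day +28). Require in Sections 5.9.3 and 6.5.4 that Week 8 be booked inside its window and no more than 28 days after the actual Week 4 visit, and change the kit size in Sections 5.4 and 5.8. With windows counted from Day 1 this leaves d4 + 5 bookable days: 1 if Week 4 is four days early, 5 if on time, 9 if four days late. Without the two spares the limit must be 27 days when Week 4 is on time or late, which leaves 4 to 8 days. The cost is two droppers per subject and tighter scheduling. It does not recover doses lost to an early Week 4, nor mend kit 1 at an on-time or late Week 4; the latter affects the Week 4 rating, not the primary comparison.

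Under either option the window anchor should be stated. Optionally, define dropper compliance in Section 5.5 as (dispensed − returned unused) / (2 × days elapsed), cross-checked with diary dose times. The dose and the twice-daily schedule do not change.
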